5.5 Significance level and confidence level

The significance level of the statistical test will be 5% (two-sides). The two-sided confidence level of the confidence interval will be 95%. The two-sided confidence level for comparison between groups will be 90%.

5.6 Descriptive statistics values to calculate

Where appropriate, continuous variables will be summarized descriptively, using the number of observations, mean, SD, median, minimum, and maximum. Categorical variables will be summarized using frequency counts and percentages.

5.7 Derived variables

(1) Definition(s) of baseline(s)

The baseline of vital signs and 12-lead ECG is the final evaluable value obtained before IMP administration on Day 1.

The baseline of body weight, BMI, Child-Pugh score and clinical laboratory values including eGFR will be the value obtained on Day -1.

(2) Age at informed consent

Age (years) = Year of informed consent - Year of birth

Subtract 1 from the age (years) calculated above, if [Month of informed consent < Month of birth] or [Month of informed consent = Month of birth AND Day of informed consent < Day of birth].

(3) BMI

BMI = Weight [kg] / (Height [m])²

Height will be the value obtained at screening.

Body weight will be the value obtained at Day -1.

The value will be rounded off at the second decimal place and reported to the first decimal place.

(4) Adverse events

The MedDRA/J version 20.0 will be used as a unified dictionary in the assessment of AEs.

(5) Adverse reactions

Adverse reactions are defined as AEs that are determined to have a “Reasonable Possibility” of causal relationship to the IMP.

6. SAMPLE SIZE AND POWER CONSIDERATIONS

The planned sample size of six evaluable subjects per hepatic impairment subjects group and per healthy subjects group is not based on a power calculation, but is according to FDA guidance for hepatic impairment PK study. Eight subjects per group will be included to obtain at least six evaluable subjects. In total, 24 subjects will be included to obtain 18 evaluable subjects.

7. STATISTICAL METHODOLOGY

7.1 Disposition of Subjects

Disposition of subjects will be listed.

- Number and percent of subjects completed and discontinued protocol scheduled visits with its reason will be presented.
- Subjects' status for each study period/phase will be summarized wherever applicable. Subjects who discontinued in each period/phase will be summarized by reasons for discontinuation.

7.2 Demographic and Other Baseline Characteristics

Major demographic and other baseline characteristics will be listed.

For each analysis set, major demographic and other baseline characteristics will be summarized by each group (Groups 1, 2 and 3) and overall. For countable values, frequency and percentage will be reported. For metric values, descriptive statistics values (number of subjects, mean, SD, minimum, median, and maximum) will be calculated.

Table. Variables related to demographic and other baseline characteristics

Category	Variable	Data format
Subject background	Sex (male, female)	Binary
	Age at consent acquisition (years)	Metric
	Height (cm)	Metric
	Weight (kg) on Day -1	Metric
	BMI on Day -1	Metric
	eGFR on Day -1	Metric
	Child-Pugh score on Day -1	Metric
	Smoking habits	Binary
	Alcohol consumption habits	Binary
	Medical history	Binary
	Complications	Binary

Child-Pugh score will be summarized only in subjects with hepatic impairment.

All data related to Child-Pugh classification will be listed.

7.3 Medical History

All medical history data will be listed.

7.4 Prior and Concomitant Medications

All medication data will be listed.

All medication data will be coded according to the latest version of WHO-DD and Anatomical Therapeutic Chemistry (ATC) classification, and will be summarized by each group (Groups 1, 2 and 3) and overall. Prior and concomitant medications will be summarized separately. Incidence tables will be summarized with ATC Level 2 code, text and Drug Code, Drug Name.

Prior medication is any medication taken within 30 days of Screening. Concomitant medication is defined as any medication, other than the IMP, which is taken during the study, including prescription and over the counter medications. All concomitant medications used from the Screening visit to the last scheduled visit must be recorded in the CRFs with their daily dosage, route, duration, and reasons for administration.

7.5 Study Drug Exposure

All exposure data will be listed.

7.6 Treatment Compliance

All compliance data will be listed.

7.7 Statistical/Analytical issues

7.7.1 Adjustments of covariates

Adjustments of covariates will not be performed.

7.7.2 Handling of Dropouts or Missing Data

Missing data, such as rejected values, will not be imputed.

7.7.3 Interim Analyses and Data Monitoring

Not applicable in the study.

7.7.4 Multicentre Studies

Not applicable in the study.

7.7.5 Multiple Comparison/Multiplicity

Adjustments of multiplicity will not be performed.

7.7.6 Use of an "Efficacy Subset" of Patients

Not applicable in the study.

7.7.7 Active-Control Studies Intended to Show Equivalence

Not applicable in the study.

7.7.8 Examination of Subgroups

Not applicable in the study.

7.7.9 Handling of Laboratory Test Values

In the case of clinical laboratory test values including equality and inequality sign, exclude equality and inequality sign and use for summarized.

7.7.10 Handling of re-examination data

For the re-examination at screening, the examination value of the re-examination at the point closest to date of IMP is adopted.

If there is unscheduled data after the date of IMP, it will be excluded from calculation of summary statistics and frequency aggregation.

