4.5 Withdrawal of individual subjects

A subject will be withdrawn if ANY of the following criteria are met:

- The subject wishes to withdraw from further participation
- The subject is significantly noncompliant with the Protocol
- The subjects is discontinued due to safety reason; continuing in the study would be detrimental to the subject's safety in the opinion of the Investigator, such as
 - The subject experiences intolerable AEs or SAEs
 - The subject has clinically significant changes in safety parameters at any of the post-dose time points, as confirmed with a repeat assessment performed as soon as possible after the initial out-of-range result

In addition, a subject may be withdrawn at any time for any reason other than those listed here.

If a subject is discontinued prematurely from the study, the date the subject is withdrawn from the study and the reason for withdrawal will be recorded on the CRF.

In case of withdrawal of a subject, the Follow-up Visit assessments should be performed, as far as possible (Section 5.2.3).

Any withdrawal due to an AE or for any safety reason should always be considered serious.

Any unresolved AE or SAE will be followed up according to Section 8.9.

In the event that a subject elects not to return to the study center for the end of study visit, the Investigator must make every effort to contact the subject to review all AEs. In the event that a subject drops out of the study at any time, the reason for discontinuation must be fully documented in the source documents and the CRF. The study center personnel will document the AEs and any other assessments in the source documents and will make every effort to complete all required end of study assessments.

Subjects withdrawn for non-treatment-related reasons may be replaced at the discretion of the Sponsor and Investigator. Replacement subjects will receive the treatments intended for the withdrawn subject.

Criteria for amendment of dose in subjects with mild hepatic impairment (Group 1)

The subjects with mild hepatic impairment will be treated first. The second subject with mild hepatic impairment will not be treated until the completion of review for safety and PK profile in the first treated subject by the Sponsor and the Investigator. [REDACTED]

[REDACTED]

Procedure and criteria for starting treatment of subjects with moderate hepatic impairment (Group 2)

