5.2.4 Unscheduled visits

An unscheduled visit is defined as any visit to the study center outside of the Protocol specified time-points due to safety reasons or when a repeated measurement is required (e.g., obvious measurement errors, measuring device failure, confirmation of out-of-range results), where the subject is seen by study personnel.

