6.7.3 Electrocardiogram

At the times indicated in the Time and Events Schedule (Table 5), a 12-lead ECG will be performed after the subject has rested for at least 5 minutes in the supine position.

The following ECG parameters will be recorded: heart rate, RR-interval, PR-interval, QRS duration, QT-interval and QTc. The QTc-interval will be calculated automatically according to Fridericia's formula. In case of results >450 ms in healthy subjects or hepatic impairment subjects, repeat measurements will be performed.

The Investigator will perform an overall evaluation of the ECG for safety purposes and the recording will be reported as 'normal', 'abnormal clinically significant (CS)', or 'abnormal

not clinically significant (NCS)'. Abnormalities of clinical significance will be reported as AEs. Repeat measurements will be performed if needed.

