6.7.4 Routine laboratory evaluations

Blood and urine samples will be collected for routine clinical laboratory safety evaluations according to Table 5. The laboratory safety evaluations performed during the study are presented in Table 8.

Additional laboratory safety evaluations will be performed at other times, if judged to be clinically appropriate, or if the ongoing review of the data suggests a more detailed assessment of laboratory safety evaluations is required.

The Investigator will perform a clinical assessment of all laboratory safety data and the recording will be reported as 'normal', 'abnormal clinically significant (CS)', or 'abnormal not clinically significant (NCS)'. Abnormalities of clinical significance will be reported as AEs. Repeat measurements will be performed if needed.

Table 8 Routine laboratory evaluations

Haematology:	
Haemoglobin	Mean corpuscular haemoglobin (MCH)
Haematocrit	Mean corpuscular haemoglobin concentration (MCHC)
Platelet count	Mean corpuscular volume (MCV)
Red blood cell (RBC) count	White blood cell (WBC) count and differential
Biochemistry:	
Alkaline phosphatase (ALP)	Uric acid
Aspartate aminotransferase (AST)	Protein (total)
Alanine aminotransferase (ALT)	Albumin
Gamma-glutamyl transpeptidase (GGT)	Cholesterol
Potassium	Triglycerides
Sodium	High density lipoprotein-cholesterol (HDL-C)
Chloride	Low density lipoprotein-cholesterol (LDL-C)
Calcium	Lactate dehydrogenase (LDH)
Inorganic phosphate	Amylase
Glucose	Creatine kinase (CK)
Blood urea nitrogen	Creatinine ^{1,2}
Bilirubin (direct and total)	Follicle stimulating hormone (FSH) ³
Coagulation:	
Prothrombin time	Activated partial thromboplastin time (aPTT)
Urinalysis:	
Specific gravity, sediment, pH, protein, glucose, ketones, urobilinogen, bilirubin, blood hCG ⁴	
Microscopic examination ⁵	
Serology:	
Hepatitis B surface antigen (HBsAg)	Human immunodeficiency virus (HIV) antigen/antibodies
Hepatitis C virus antibody (HCVAb)	
Drugs and alcohol screen:	
Phencyclidine, cocaine, barbiturates, tetrahydrocannabinol, benzodiazepines, amphetamines/methamphetamines, opiates, and alcohol breath test	

¹ eGFR will be calculated using the 3-variable Japanese equation² eCLcr will be calculated using the Cockcroft-Gault formula³ Females only; performed at Screening only⁴ Females only; a urine pregnancy test will be performed at Screening, Day -1 and follow-up⁵ Performed only if required, based on urinalysis results

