13. REVISION HISTORY FOR SAP AMENDMENTS

Version 2.0 (9 October, 2018)

It reflected the results of the data review meeting on 25 September, 2018.

In Section 5.3, the PK analysis excluding possible outliers conduct for secondary/sensitivity analysis has been added.

In Section 7.7.10, a description concerning the Handling of re-examination data has been added.

In Section 7.9.1, the method to calculate the duration of the AE and the time from start of the IMP to AE occurrence has been changed from date to date/time.

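### SAP 7.7.10 keeps unscheduled data after the dosing date out of the safety tables, so a valid unscheduled repeat cannot replace a faulty reading and a peak seen only at an unscheduled visit may not be tabulated

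*SAP*

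**What the plan says.** SAP 7.7.10 has two rules. For re-examinations at screening, the value closest to dosing is used. For data after dosing: "If there is unscheduled data after the date of IMP, it will be excluded from calculation of summary statistics and frequency aggregation". No exception is given.

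Protocol 5.2.4 defines an unscheduled visit as one "outside of the Protocol specified time-points due to safety reasons or when a repeated measurement is required". Its examples are "obvious measurement errors, measuring device failure, confirmation of out-of-range results".

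The protocol expects such data to arise:
- Section 6.7.4: "Additional laboratory safety evaluations will be performed at other times, if judged to be clinically appropriate".
- Section 6.7.3, on QTc: "In case of results >450 ms in healthy subjects or hepatic impairment subjects, repeat measurements will be performed".
- Section 4.5 makes one withdrawal criterion depend on a significant change "as confirmed with a repeat assessment performed as soon as possible after the initial out-of-range result".

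The revision history in SAP section 13 places the rule in version 2.0 of 9 October 2018, which reflects the data review meeting of 25 September 2018: "In Section 7.7.10, a description concerning the Handling of re-examination data has been added".

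**The concern.** Unscheduled post-dose data are mostly collected because a value looked wrong or a subject looked unwell. A blanket exclusion removes from the tables the readings taken for those reasons.

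Two things are at stake. The first is the accuracy of the by-visit summaries when a scheduled reading is known to be bad and a good repeat exists. The second is whether the tables show the largest post-dose change in each subject. Safety and tolerability is the study's secondary objective. Protocol 8.5 also notes that, in subjects with hepatic disease, change from baseline is an important indicator because their values may already lie outside the normal range.

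**Working it through.** The plan states no figure for this rule, so the check sets the sections side by side and adds simple illustrations.

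**1. A faulty scheduled reading after dosing**
- Protocol 10.3.2 leaves the handling of missing, unused and spurious data to the SAP. SAP 5.3 covers invalid PK data. There is no matching section for safety data.
- If the faulty reading is kept, it enters the mean.
- If it is rejected, SAP 7.7.2 leaves it missing without imputation.
- In both cases SAP 7.7.10 bars a valid repeat that counts as unscheduled.
- Before dosing the logic runs the other way. Protocol 5.2.1 (screening) and 5.2.2.1 (Day -1) let the latest assessment replace the earlier one, and the first rule in SAP 7.7.10 does the same for screening. The SAP gives no reason for the difference.

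Illustration with assumed values: a potassium of 7.0 mmol/L is recorded in error and the valid repeat is 4.2, in a group of 8.
- Kept: the group mean shifts by (7.0 − 4.2)/8 = 0.35 mmol/L.
- Rejected: no error in the mean, but n falls from 8 to 7 at that time point.
- Repeat used: neither loss occurs.

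**2. A peak seen only at an unscheduled visit**
- SAP 5.2 gives the post-dose safety time points as 24 h, 48 h and follow-up on Day 7 (+2 days). Protocol Table 9 counts 5 samples each for haematology, biochemistry and coagulation. Taking screening and Day -1 as the 2 pre-dose samples leaves 5 − 2 = 3 post-dose samples, which agrees.
- The interval from Day 3 to follow-up is 7 − 3 = 4 days to 9 − 3 = 6 days. A value taken in it can only be unscheduled.
- SAP 7.9.2 builds shift tables on scheduled visits. The table list in SAP 12.2 has no worst post-dose or any-time summary for laboratory or ECG data.
- Such a value therefore cannot enter the laboratory or ECG maxima, or the clinical-assessment or overall-evaluation frequencies. By contrast, a Group 2 progression criterion in Protocol 4.5 counts transaminase and bilirubin elevations at any point after treatment.

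Illustration: one subject is 1/8 = 12.5 percentage points of a full group, or 1/6 = 16.7 points at the minimum of 6 evaluable. This is the weight of any subject in any table. It does not measure bias.

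The documents give no rate for such values. If the per-subject chance is p, the chance of at least one among the 16 subjects with hepatic impairment is 1 − (1 − p)^16. This gives 28%, 56%, 81% and 97% for assumed p of 2%, 5%, 10% and 20%. The range is too wide to carry weight.

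**3. Scope of the rule**
- It refers to data after the date of dosing. On its wording, this does not clearly include readings later on Day 1.
- Subjects are confined until Day 3, and SAP 5.2 allows ±1 hour at 24 h and 48 h (for urinalysis, up to 1 hour after). The SAP does not say whether a prompt repeat inside that window is unscheduled.

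**The case against.** The case on the other side is substantial.

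- **The values are not lost.** SAP 7.9.2 to 7.9.4 list all laboratory, vital-sign and ECG data, and 7.9.2 adds a listing for subjects with clinically significant laboratory findings. With 24 subjects these can be read in full. This stands.
- **Clinically significant peaks reach a summary.** Protocol 6.7.2 to 6.7.4 and 8.5 make clinically significant abnormalities adverse events, and the TEAE tables are not tied to scheduled visits. This stands too. What is missing is the numerical maximum, and any large change that the investigator does not rate as clinically significant.
- **An any-time frequency row would use that same investigator rating.** True, which is why a worst-value summary is also needed: it does not depend on the rating.
- **Scheduled-only by-visit statistics are sound.** They follow Protocol 10.3.5.4 and 10.3.5.5, which ask for summaries at each time point, and they avoid over-weighting subjects measured more often. This stands, and the fix keeps them.
- **An unscheduled value need not be the worst.** Where a repeat only confirms a high scheduled reading, that reading is already in the table. The second consequence is therefore conditional.

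A reader might go further and infer that known errors necessarily stay in the means. The documents do not say so: SAP 7.7.2 allows for rejected values, and the data review meeting in SAP section 4 decides data handling. A reader might also infer from the version 2.0 date that the rule was shaped by the results. SAP section 4 planned that meeting to settle handling rules, with version 1.0 fixed beforehand, so recording its outcome in version 2.0 follows the stated process.

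**Conclusion.** The point holds as a cheap improvement. As written, SAP 7.7.10 prevents a valid unscheduled repeat from being used after dosing, whether the faulty scheduled reading is kept or rejected. It also leaves no table in which a laboratory or ECG peak seen only at an unscheduled visit can appear.

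The harm is moderate, because the listings hold every value and the TEAE tables capture what the investigator rates as clinically significant. Nothing in the documents shows that any subject was affected. The 12.5-point and 0.35 mmol/L figures only illustrate how much one subject or one reading weighs in a group of 8.

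The conclusion assumes that the repeat or extra reading counts as unscheduled and falls after the dosing date. The SAP leaves both unclear for later Day 1 readings and for repeats within the ±1 hour window. A reading of the rule as removing every post-dose repeat would therefore go too far.

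**What to change.** 1. Keep the by-visit summaries on scheduled data.
2. Amend SAP 7.7.10 so that, where a scheduled post-dose reading is documented as a measurement or device error, the valid repeat for that time point replaces it.
3. Add a worst post-dose (any-time) summary for AST, ALT, bilirubin, creatinine and QTcF that includes unscheduled values.
4. Add an any-post-dose-time row, also including unscheduled values, to the clinical-assessment and overall-evaluation frequencies.
5. State whether the rule covers readings later on Day 1 and repeats taken within the ±1 hour window.
6. Say in the study report whether any subject's data were affected by the rule.

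The cost is a few SAP lines and table rows, using data already collected and listed. The small downside is that a worst value is not tied to one time point and tends to be more extreme in subjects measured more often. A footnote giving the number of unscheduled values included would make this visible.

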7.8 Pharmacokinetic Assessments

7.8.1 Analysis of Individual Plasma Concentrations

All measured plasma concentrations will be listed.

Plasma concentrations will be summarized at each scheduled sampling time point by each group (Groups 1, 2 and 3). The following descriptive statistics will be calculated: N (number of subjects), n (number of valid observations), arithmetic mean, SD, CV%, minimum, median, maximum, geometric mean and geometric CV%. Nominal sampling times will be displayed in the summary. For the calculation of the descriptive statistics other than geometric mean and geometric CV%, concentration values reported as BLQ will be set to 0. For the calculation of the geometric mean and geometric CV%, concentration values reported as BLQ will be set to $\frac{1}{2}$ of LLOQ.

CV% and Geometric CV% will be calculated as follows:

$$CV\% = \frac{SD}{\text{arithmetic mean}} \times 100$$

$$\text{Geometric CV\%} = [\exp(\sigma^2) - 1]^{1/2} \times 100$$

where σ represents the SD computed on the natural logarithmic transformed concentrations.

To visualize the concentration-time profiles of each group, the following plots will be produced in linear and semi-logarithmic scales:

1. Individual subject concentration-time plot for each group (Groups 1, 2 and 3) overlaid in one graph.
2. Mean concentration-time plot for each group (Groups 1, 2 and 3) overlaid in one graph.

In the summary tables, arithmetic mean, SD, minimum, median, maximum and geometric mean will be presented with the number of significant digits which individual concentrations are reported. In addition, CV%, and geometric CV% will be presented with 1 decimal place.

7.8.2 Analysis of Pharmacokinetic Parameters

All PK parameters will be listed.

The PK parameters will be summarized by each group (Groups 1, 2 and 3). The following descriptive statistics will be calculated: N (number of subjects), n (number of valid observations), arithmetic mean, SD, CV%, minimum, median, maximum, geometric mean and geometric CV%.

For the descriptive statistics, the minimum and maximum will be presented according to following requirement:

- [REDACTED]
- C_{\max} : will be presented with the number of significant digits they are reported with.
- [REDACTED]
- Other PK parameters: will be presented with a fixed number of decimal places for each parameter. The number of decimal places is 2 decimal places corresponding to having 3 significant digits at the minimum by analyte.

Mean, SD, median and geometric mean will be presented with the number of decimals as follows.

- C_{\max} : will be presented with 4 significant digits.
- Other PK parameters: will be presented with 2 decimal places.

CV% and geometric CV% will be presented with 1 decimal place.

To visualize the relationship between measures of hepatic function and between the PK parameters of MCI-186 and the sulfate conjugate, the following scatter plots of $AUC_{0-\text{last}}$, $AUC_{0-\infty}$, [REDACTED] and C_{\max} (on the vertical axis) versus Child-Pugh score, Child-Pugh classification (Normal, Mild, Moderate), albumin, bilirubin, prothrombin and eGFR (on the horizontal axis) with regression line, will be produced in linear scales:

1. The PK parameters of ($AUC_{0-\text{last}}$, $AUC_{0-\infty}$, [REDACTED] and C_{\max} of MCI-186 and the sulfate conjugate) vs (Child-Pugh score, Child-Pugh classification, albumin, bilirubin, prothrombin time and eGFR) plot will be produced for all subjects overlaid in one graph.

Child-Pugh score will be plotted only in subjects with hepatic impairment.

Regarding the log-transformed values of $AUC_{0-\text{last}}$, $AUC_{0-\infty}$ and C_{\max} of MCI-186 and the sulfate conjugate, analysis of variance (ANOVA) will be performed with groups as factors.

The estimated LSmeans and associated two-sides 95% confidence intervals for these PK parameters in each group, and the estimated LSmeans and associated two-sided 90% confidence intervals for the differences of each the hepatic impairment group (Group 1 or 2) compared to the normal hepatic function group (Group 3) will be calculated.

The calculated values will be retransformed using antilogarithms and displayed.

